7 STATISTICAL ANALYSIS

The Full Analysis Set (FAS) population will be used to summarize the primary and all secondary endpoints (excluding radiographic assessments) while the Safety (SAF) population will be used summarize all safety and exploratory endpoints. The SAF population will additionally be used to summarize radiographic assessments The Per Protocol (PP) population will additionally be used to summarize the primary endpoint.

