7.2 Analysis Populations

The following section details the analysis populations:

TMP-CD-30-01 Statistical Analysis Plan - Revision B; SOP-CD-30 Statistical Analysis

CONFIDENTIAL AND PROPRIETARY

This document contains information that is confidential and proprietary to Smith & Nephew PLC and Smith & Nephew, Inc. and is intended for use only by Smith+Nephew and its manufacturer. It shall not be reproduced or copied in whole or in part, nor shall the contents be disclosed by any means without prior written permission from Smith+Nephew, nor shall anyone make any use of it that is contrary to the expressed or implied wishes of Smith+Nephew.

Statistical Analysis Plan

A Prospective, Multi-center, Randomized, Controlled Study to Evaluate theVersion: 2.0,Safety and Efficacy of the OR3O[™] Dual Mobility System versus conventional29-Feb-2024single bearing design Total Hip System in Primary Total Hip Arthroplasty (THA)Page: 13 of 27ProceduresProcedures

Number: OR3O.2019.10 ST: 1100 Version: 2.0, 29-Feb-2024 Page: 13 of 27

Safety (SAF) Population: This is defined as all hips who have been implanted with the OR3O[™] Dual Mobility System or controlled system. The SAF population will be based on the device that is implanted into the hip and not the one the hip is randomized to (if different).

Full Analysis Set (FAS) Population: This is defined according to the basic principle of Intent-to-Treat (ITT) principle i.e., all implanted hips with at least one postoperative effectiveness, HRQoL or performance will be included in FAS Population.

Per-Protocol (PP) Population: The PP population is the subset of hips in the FAS population who do not have major protocol deviations and who satisfied all enrollment eligibility criteria. Criteria that can be regarded as major deviations will be formally classified on a case-by-case basis prior to the final study database lock.

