7.7 Protocol Deviations

A listing of deviations encountered on-study will be listed. Major protocol deviations that are deemed significant which will subsequently lead to the exclusion of subjects in the PP population will be appropriately identified and flagged.

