7.10 Analysis of Primary Endpoint

The analysis of the primary endpoint will utilize hypothesis testing in two steps. First, testing for non-inferiority of P1 versus P0 and secondly if non-inferiority is demonstrated then testing for superiority of P1 to P0 as follows:

H0 (null): P1 \leq (P0- Δ) versus Ha1 (alternate 1st stage): P1 > (P0- Δ) and Ha2 (alternate 2nd stage): P1 > P0,

Where Δ is the margin of non-inferiority (9.5%), P1 is the proportion of good to excellent HHS scores at 12 months in the OR3O dual mobility system (test) and P0 is the proportion of good to excellent HHS scores at 12 months in the Conventional, single-bearing design (control).

- The null hypothesis, H0, is rejected in favor of the first alternate hypothesis, Ha1, (i.e. demonstration of non-inferiority) if the lower limit of the 95% Confidence interval for P1p0 > $-\Delta$) otherwise, H0 will be accepted.
- If the null hypothesis, H0, is rejected and in favor of Ha1, the test for superiority would be performed. If the upper limit of the 95% CI for P0 is less than the lower limit of the 95% CI for P1, then superiority of P1 to P0 is demonstrated, i.e. acceptance of Ha2.. This stepwise hypothesis-testing framework would not require any adjustment made to a, thus strongly controlling the overall significance at 0.05. All 95% CIs generated for P1 and P0 would be calculated using exact methods.

However, as this study has been early terminated the study no longer has sufficient power for this test to be relevant and it will therefore not be performed. Summary statistics for P1 and P0 will be reported.

The primary endpoint will be summarized using the SAF population.

CONFIDENTIAL AND PROPRIETARY

This document contains information that is confidential and proprietary to Smith & Nephew PLC and Smith & Nephew, Inc. and is intended for use only by Smith+Nephew and its manufacturer. It shall not be reproduced or copied in whole or in part, nor shall the contents be disclosed by any means without prior written permission from Smith+Nephew, nor shall anyone make any use of it that is contrary to the expressed or implied wishes of Smith+Nephew.

Statistical Analysis Plan

A Prospective, Multi-center, Randomized, Controlled Study to Evaluate the
Safety and Efficacy of the OR3O™ Dual Mobility System versus conventional
single bearing design Total Hip System in Primary Total Hip Arthroplasty (THA)Version: 2.0,
29-Feb-2024
Page: 22 of 27ProceduresPage: 22 of 27

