7.11 Analysis of Secondary Endpoints

All secondary endpoints will be summarized using the SAF analysis population. Changes from preoperative to postoperative will not be analysed for PROMs due to early termination of the study. Summary statistics for observed PROMs score would be presented.

Implant Survivorship

- Survivorship of the OR3O Dual Mobility System (assessed by revision for any reason) will be summarized using Kaplan-Meier survival tables and graphs. Time to revision will be the endpoint of interest, for subjects who die, are lost to follow-up or do not encounter the event of interest by the time of study termination would be censored on these dates.
- Survivorship of the controlled system up to 2 years after surgery (assessed by revision for any reason), Kaplan-Meier survival tables analogous to that specified for the OR3O Dual Mobility system will be implemented here as well.

Harris Hip Score (HHS)

- HHS scores for each subject will further be categorized as follows: Excellent (90-100); Good (80-89); Fair (70-79); Poor (60-69) and; Very poor (<60). Shift tables from the preoperative visit to all postoperative visits using these classifications will be generated.
- The total HHS and the scores for each of its following subdomains: pain, function, absence of deformity, and range of motion will be summarized using continuous summary characteristics by preoperatively and postoperatively at 6 weeks, 3 months, 6 months, 1 year and 2 years (i.e. by visit). For the HHS and its subdomain scores, independent repeated measurement Analysis of Covariance (ANCOVA) model (with visit as the repeated term) will be used to model the change from preoperative to postoperative with total HHS (and its

CONFIDENTIAL AND PROPRIETARY

This document contains information that is confidential and proprietary to Smith & Nephew PLC and Smith & Nephew, Inc. and is intended for use only by Smith+Nephew and its manufacturer. It shall not be reproduced or copied in whole or in part, nor shall the contents be disclosed by any means without prior written permission from Smith+Nephew, nor shall anyone make any use of it that is contrary to the expressed or implied wishes of Smith+Nephew.

Statistical Analysis Plan

A Prospective, Multi-center, Randomized, Controlled Study to Evaluate the
Safety and Efficacy of the OR3O™ Dual Mobility System versus conventional
single bearing design Total Hip System in Primary Total Hip Arthroplasty (THA)Version: 2.0,
29-Feb-2024

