7.12 Analysis of Exploratory Endpoints

Survivorship of compatible components up to 2 years

Survivorship of acetabular shell, femoral head, and any of the femoral stems will be estimated by cumulative proportion of hips without revision of the respective components due to any reason, up to 2 years. The cumulative implant survival rates will be summarized using KM product limit estimates. This will be summarized using the SAF analysis population.

Dislocation percentage of the hip up to 2 years after device implantation

The cumulative dislocation percentage at the interim visits up to 2 years after device implantation, $p_{dis,i}$ will be compared to a literature specified percentage, $p_{literature}$. These literature-specified

CONFIDENTIAL AND PROPRIETARY

This document contains information that is confidential and proprietary to Smith & Nephew PLC and Smith & Nephew, Inc. and is intended for use only by Smith+Nephew and its manufacturer. It shall not be reproduced or copied in whole or in part, nor shall the contents be disclosed by any means without prior written permission from Smith+Nephew, nor shall anyone make any use of it that is contrary to the expressed or implied wishes of Smith+Nephew.

Statistical Analysis Plan

A Prospective, Multi-center, Randomized, Controlled Study to Evaluate the
Safety and Efficacy of the OR3O[™] Dual Mobility System versus conventional
single bearing design Total Hip System in Primary Total Hip Arthroplasty (THA)Version: 2.0,
29-Feb-2024
Page: 25 of 27ProceduresProcedures

Number: OR3O.2019.10 ST: 1100 Version: 2.0, 29-Feb-2024 Page: 25 of 27

percentages will be specified prior to database lock for final analyses. For the estimation of dislocation rate, a hip with multiple dislocations on-study will be counted only once. Two-sided exact 95% CIs will be estimated for p_{dis,i} where i is the visit at which the cumulative dislocation will be estimated (i.e. at 3months, 6 months, 1 year and 2 years). This will be summarized using the SAF population. One of the following conclusions will be made:

- If the lower limit (LL) of the two-sided 95% CI for $p_{dis,i}$ is > $p_{literature}$, then it is concluded that the dislocation rate on-study is significantly greater than the literature-specified rate.
- If the upper limit (UL) of the two-sided 95% CI for $p_{dis,i} < p_{literature}$, then it is concluded that the dislocation rate on-study is significantly less than than the literature-specified rate.

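### SAP v2.0 puts the primary and non-radiographic secondary endpoints on FAS in Section 7 but on the as-implanted SAF in 7.10 and 7.11, and 7.15 records no change of population from the protocol

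*SAP*

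**What the plan says.** SAP Section 7 opens with a general allocation: "The Full Analysis Set (FAS) population will be used to summarize the primary and all secondary endpoints (excluding radiographic assessments". It adds: "The Per Protocol (PP) population will additionally be used to summarize the primary endpoint". It reserves SAF for safety, exploratory and radiographic summaries.

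The endpoint sections say otherwise. SAP 7.10: "The primary endpoint will be summarized using the SAF population", with no mention of PP. SAP 7.11: "All secondary endpoints will be summarized using the SAF analysis population".

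SAP 7.2 defines the two sets differently. For SAF: "The SAF population will be based on the device that is implanted into the hip and not the one the hip is randomized to". FAS invokes the intent-to-treat principle and adds a data requirement: "all implanted hips with at least one postoperative effectiveness, HRQoL or performance will be included in FAS Population".

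Protocol 10.4.1 names ITT as the main population for the primary endpoint, with PP as a sensitivity analysis. Protocol 10.4.2 names ITT for all secondary endpoints. SAP 7.15, the section for departures from the protocol, says only that testing is replaced by descriptive statistics because the study ended early. Protocol 11.9 requires changes to the statistical plan, and the reasons for them, to be recorded in the SAP.

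**The concern.** A programmer working from this SAP has two incompatible instructions for the same table. The choice decides whether P1 and P0 compare hips as randomised or as treated. The text provides for the two to differ, because the SAF rule exists for hips whose implanted device is not the assigned one. Readers of a randomised trial will expect the efficacy display to follow randomisation, and the protocol told them it would. If 7.10 and 7.11 are followed, that changes with no stated reason.

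**Working it through.** The plan gives no figure to reproduce here. The check is a comparison of the texts, followed by an illustration of size.

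**Populations side by side**

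| Endpoint group | Protocol 10.4–10.5 | SAP Section 7 | SAP 7.10–7.13 |
|---|---|---|---|
| Primary | ITT; PP as sensitivity | FAS; PP in addition | SAF; PP not mentioned |
| Secondary, non-radiographic | ITT | FAS | SAF |
| Radiographic | ITT (within all secondary) | SAF | SAF |
| Exploratory | none stated | SAF | SAF |
| Safety | SAF | SAF | SAF |

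Protocol 10.2 defines SAF, FAS and PP but no separate ITT set. It describes FAS as following the ITT principle, and Protocol 10.3 lists SAF, ITT and PP as the three sets. The protocol's ITT is therefore best read as FAS. This is an inference, though a natural one.

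**Each reading in turn**

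- If Section 7 governs, the population sentences in 7.10 and 7.11 are wrong.
- If 7.10 and 7.11 govern, every endpoint in 7.10 to 7.13 is on SAF (7.12, for example, says "This will be summarized using the SAF population"). FAS and PP are then defined but serve no endpoint. SAP 7.7 still flags deviations for PP: "Major protocol deviations that are deemed significant which will subsequently lead to the exclusion of subjects in the PP population". In addition, 7.15 omits a departure from the protocol.

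Either way an edit is needed.

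**Where FAS and SAF can differ.** Both sets contain implanted hips only. They differ for (a) implanted hips with no postoperative data and (b) hips given the other arm's device.

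(a) *No postoperative data.* SAP 7.3 counts a missing primary endpoint as a failure when there is nothing to carry forward. SAF keeps such a hip as a failure; FAS omits it. Take the planned 85 per arm and roughly the 95% success of SAP 6.1, with 80 successes, 4 observed failures and 1 hip without data:

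- FAS: 80/84 = 95.24%
- SAF: 80/85 = 94.12%
- Difference: 1.12 points

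Arm sizes after early termination are not given. At an assumed 40 per arm the same single hip costs 37/39 − 37/40 = 94.87% − 92.50% = 2.37 points. At an assumed 20 it costs 18/19 − 18/20 = 94.74% − 90.00% = 4.74 points. If P1 and P0 were computed on observed scores only, the difference would be 0.

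(b) *Crossover.* Start with 81/85 in each arm, so that P1 − P0 = 0 as randomised, and regroup one hip from test to control:

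- the hip is a failure: 81/84 − 81/86 = 96.43% − 94.19% = +2.24 points
- the hip is a success: 80/84 − 82/86 = 95.24% − 95.35% = −0.11 points

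If the crossover hip is a random draw from the 85, the expected shift is (4/85)(2.2425) + (81/85)(−0.1107) = 0.1055 − 0.1055 = 0.

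The HHS, EQ-5D-5L and HOOS JR summaries use observed scores, so at postoperative visits they differ between the two sets only through (b).

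**The case against.** The strongest reply is that this is a consistency edit to descriptive tables. All testing is cancelled, no crossover or hip without postoperative data is reported, and a crossover at random shifts nothing on average. That stands, and it limits the size of the point. It does not remove the contradiction.

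A second reply is that the specific section should govern, or that early termination explains the change. The supplied text has no precedence rule. The SAP gives termination as the reason for dropping tests and change-from-baseline analyses, but never for changing a population.

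A third reply is that the change may be recorded elsewhere. Protocol 11.9 asks for a record in the SAP, not specifically in 7.15, and the front pages removed from the public text could hold a revision history. This cannot be excluded. A reader might infer that the sponsor changed the population without disclosing it; the documents do not support that. Even so, a record elsewhere would leave Section 7 in conflict with 7.10 and 7.11.

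A fourth reply is that FAS is not closer to intent-to-treat in every respect. It drops implanted, randomised hips with no postoperative data, which SAF with the 7.3 rule would keep as failures. This is correct and is the real cost of the fix. Nor is it a fault that 7.10 does not repeat the 7.3 rule: on its face that rule still covers the primary endpoint, and nothing withdraws it.

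**Conclusion.** The concern holds as an internal contradiction: SAP v2.0 gives two populations for the primary and non-radiographic secondary endpoints. The version in 7.10 and 7.11 departs from the protocol's ITT without an entry in 7.15. It should be fixed.

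The effect is confined to the reported P1, P0 and secondary summaries. There is no type I error consequence, because no hypothesis will be tested. The size is unknown: it is zero if there are no crossovers and no implanted hips without postoperative data. It is about 1.1 points per hip without data in an 85-hip arm, assuming about 95% success and that 7.3 applies, and more per hip in smaller arms.

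A reader might infer from the single-failure case (+2.24 points) that as-implanted grouping favours the test device. The documents do not support this. They report no crossover, and a systematic shift would require crossover to be related to outcome.

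**What to change.** - In SAP 7.10, and in 7.11 for the non-radiographic secondary endpoints, replace SAF with FAS analysed as randomised, in line with Section 7.
- Keep the PP summary of the primary endpoint and name it in 7.10.
- Keep SAF for safety, exploratory and radiographic data. If implant survivorship is to stay on SAF, edit Section 7 to say so; otherwise the contradiction returns.
- List in 7.15, with reasons, every population that differs from the protocol. This includes radiographic data on SAF, since Protocol 10.4.2 puts all secondary endpoints on ITT.

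The cost is SAP wording and an as-randomised flag in the analysis data. SAP Section 2 already provides for an addendum or amended SAP. No protocol change or new data are needed. The downside is that FAS omits implanted hips with no postoperative data, so their number should be reported by arm.

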7.11 Analysis of Secondary Endpoints

All secondary endpoints will be summarized using the SAF analysis population. Changes from preoperative to postoperative will not be analysed for PROMs due to early termination of the study. Summary statistics for observed PROMs score would be presented.

Implant Survivorship

- Survivorship of the OR3O Dual Mobility System (assessed by revision for any reason) will be summarized using Kaplan-Meier survival tables and graphs. Time to revision will be the endpoint of interest, for subjects who die, are lost to follow-up or do not encounter the event of interest by the time of study termination would be censored on these dates.
- Survivorship of the controlled system up to 2 years after surgery (assessed by revision for any reason), Kaplan-Meier survival tables analogous to that specified for the OR3O Dual Mobility system will be implemented here as well.

Harris Hip Score (HHS)

- HHS scores for each subject will further be categorized as follows: Excellent (90-100); Good (80-89); Fair (70-79); Poor (60-69) and; Very poor (<60). Shift tables from the preoperative visit to all postoperative visits using these classifications will be generated.
- The total HHS and the scores for each of its following subdomains: pain, function, absence of deformity, and range of motion will be summarized using continuous summary characteristics by preoperatively and postoperatively at 6 weeks, 3 months, 6 months, 1 year and 2 years (i.e. by visit). For the HHS and its subdomain scores, independent repeated measurement Analysis of Covariance (ANCOVA) model (with visit as the repeated term) will be used to model the change from preoperative to postoperative with total HHS (and its

CONFIDENTIAL AND PROPRIETARY

This document contains information that is confidential and proprietary to Smith & Nephew PLC and Smith & Nephew, Inc. and is intended for use only by Smith+Nephew and its manufacturer. It shall not be reproduced or copied in whole or in part, nor shall the contents be disclosed by any means without prior written permission from Smith+Nephew, nor shall anyone make any use of it that is contrary to the expressed or implied wishes of Smith+Nephew.

Statistical Analysis Plan

A Prospective, Multi-center, Randomized, Controlled Study to Evaluate the
Safety and Efficacy of the OR3O™ Dual Mobility System versus conventional
single bearing design Total Hip System in Primary Total Hip Arthroplasty (THA)Version: 2.0,
29-Feb-2024
Page: 23 of 27ProceduresProcedures

Number: OR3O.2019.10 ST: 1100 Version: 2.0, 29-Feb-2024 Page: 23 of 27

subdomain) scores as dependent variable (s). As a minimum, each model will contain treatment (OR3O dual mobility system i.e. Test, versus Conventional single-bearing design, i.e. Control) and a repeated visit as fixed effect terms. Preoperative prognostic and demographic variables including but not only restricted to type of THA procedure (primary), age, BMI, sex, and investigational site and any other covariate that can be ascertained to be impactful on the total HHS (or its subdomain scores) will be introduced as covariates in the model. These covariates will be added to the model in a stepwise manner and retained in the final model if a p-value of \leq 0.1 is encountered. Model based means (adjusted means or Least Square Means, LSMeans) and corresponding standard errors associated with the change from preoperative to postoperative HHS (and its subdomain) scores by treatment will be presented. Model based differences (and corresponding standard errors) between treatment as well as their corresponding 95% CIs will additionally be summarized.

 However, as this study has been early terminated there is not sufficient data for the change from baseline analysis. Thus, only summary statistics of the observed score would be presented.

EQ5D-5L Score

- The HRQoL Index score and its VAS component will be sumarized using summary statistics for continuous variables preoperatively and at the postoperative visits: 6 weeks, 3 months, 6 months, 1 year and 2 years (i.e. by visit). Model based repeated measures ANCOVA analysis, which specified for the total HHS and its subdomain scores will be implemented.
 - However, as this study has been early terminated there is not sufficient data for the change from baseline analysis. Thus, only summary statistics of the observed score would be presented.

Hip Disability and Osteoarthritis Outcome Score for Joint Replacement (HOOS JR.)

CONFIDENTIAL AND PROPRIETARY

This document contains information that is confidential and proprietary to Smith & Nephew PLC and Smith & Nephew, Inc. and is intended for use only by Smith+Nephew and its manufacturer. It shall not be reproduced or copied in whole or in part, nor shall the contents be disclosed by any means without prior written permission from Smith+Nephew, nor shall anyone make any use of it that is contrary to the expressed or implied wishes of Smith+Nephew.

Statistical Analysis Plan

A Prospective, Multi-center, Randomized, Controlled Study to Evaluate theVersion: 2.0,Safety and Efficacy of the OR3O[™] Dual Mobility System versus conventional29-Feb-2024single bearing design Total Hip System in Primary Total Hip Arthroplasty (THA)Page: 24 of 27ProceduresProcedures

- Number: OR3O.2019.10 ST: 1100 Version: 2.0, 29-Feb-2024 Page: 24 of 27
- The transformed (0-100) interval scores will be summarized by visit using descriptive summary characteristics for continuous variables. Changes from preoperative to postoperative follow-up time points will similarly be summarized. Model based repeated measures ANCOVA analysis, the type previously specified for the total HHS (and its subdomain scores) will be implemented.
 - However, as this study has been early terminated there is not sufficient data for the change from baseline analysis. Thus, only summary statistics of the observed score would be presented.

Radiographic Characteristics

• The radiographic characteristics of implant position, implant fixation, heterotopic ossification, radiolucencies, osteolysis, atrophy and hypertrophy will be summarized using descriptive characteristics for continuous or categorical variables as appropriate and relevant by visit.

